16. DATA ANALYSIS PLAN

Missing Data

All efforts will be made to prevent missing data. Due to the exploratory nature of the study, missing data will not be accommodated statistically.

Sample Size Estimation

We plan to recruit 52 people for this study because it is what we think is feasible given our resources and should provide sufficient information to determine whether there is a reasonable potential efficacy signal to move forward to a randomized clinical trial.

Aim1. Feasibility Analyses

(1) Descriptive statistics will be used to summarize all feasibility outcomes. (2) Common themes in subject-reported reasons for low adherence will be summarized in the qualitative data.

Aim 2. Preliminary Efficacy

- (1) Primary preliminary efficacy: Preliminary efficacy for the water volume displacement outcome and the Edema Symptom Daily Diary will be assessed using Wilcoxon sign-ranked test comparing the outcomes from Baseline and Treatment Endpoint.
- (2) Secondary preliminary efficacy: Similar analyses to those in the primary preliminary efficacy aim will be used for the secondary efficacy outcomes.

Due to the exploratory nature of the study, no adjustments will be made for multiplicity.

Exploratory Analyses

- 1) Similar analyses to those in the primary preliminary efficacy aim will be used to assess changes between Baseline and Treatment Period Endpoint for the continuous exploratory efficacy outcomes.
- 2) The percentage of subjects whose monofilament threshold improves between Baseline and Double-blind Endpoint will be compared using a Fisher's exact test.
- 3) Trajectories of changes in activity (measured via the Fitbit) and changes in swelling (measured via NRS swelling and symptoms ratings) will be visually inspected and compared to investigate whether increased activity precedes and therefore may contribute to decreased swelling.
- 4) Qualitative analysis techniques will be used to analyze the cognitive interview data to improve self-report measurements for peripheral edema.

Page 24 of 26

5) We will explore the data for patterns to see if people with different causes of edema seem to benefit from the treatment more frequently than others. These qualitative analyses will be used to inform future entry criteria.

REFERENCES

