(1) Swelling and symptoms associated with edema will be recorded in the Edema Symptom Daily Diary using a verbal rating scale (VRS) of swelling in the lower limbs and feet using the anchors "none", "a little bit", "quite a bit" "a lot", or "very much", [1 = none, 5 = very much]. The subject will also be asked to rate these symptoms, while thinking about the past week using the Edema Symptom Inventory-Week Recall, which uses the same scale as the diary and the Edema Symptom Inventory-Week Recall 0 – 10 Scale which uses 0 – 10 numerical rating scale (NRS) [0 = not at all, 10 = worst imaginable].

Potential Efficacy (secondary) Objective

assessments:

Page 4 of 26

(1) Swelling. The coordinator will use a tape measure at the arch of the foot, 1/2 and the distance between the middle of the kneecap and the ankle, and at the knee crease of both limbs regardless of which is more affected. Measurements will be recorded in the **Coordinator Lower Limb Swelling** form. Tape measurements have been used in a successful trial of compression stockings for flight-induced peripheral edema.¹²

Patient reported outcome measures (PROs):

- (1) Changes in symptoms, activity, and emotions will be recorded in the **Impression of Change in Edema Symptoms** form that uses a verbal rating scale (VRS) asking subjects to report whether they have experienced changes in the symptoms. The scale uses the anchors "very much improved", "much improved", "minimally improved", "not changed", "minimally worse", "much worse", or "very much worse" [1 = very much improved, 7 = very much worse].
- (2) Quality of Life will be assessed using the Lymphoedema Quality of Life Tool (LYMQOL) using a verbal rating scale (VRS) with anchors "not at all", "a little bit", "quite a bit", or "very much [1 = not at all, 4 = very much]. If the question is not applicable the measurable scale value is 0. Overall quality of life (Q22) is measured using a 0 10 numerical rating scale NRS scores [0 = poor, 10 = excellent]. The LYMQOL was developed based on interviews with patients. The initial validation study found reasonable Chronbach's alpha for items and criterion validity when compared to a general measure of quality of life. 13

Potential Efficacy (exploratory) Objective

assessments:

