Visit 2- Baseline visit: (In-person / Day 0 up to + 5_days)

The coordinator will download the Quell App to the subject's mobile device, setup a Quell Health account for the subject (using valid de-identified study email address and password) and help them pair the TENS device to their mobile device and calibrate it. They will introduce the concept of TENS and describe how it is likely to feel to the subjects using a standardized script. They will give the subject 2 electrode strips along with the TENS device, which should be sufficient for the 3-week duration of the treatment period of the study. They will provide the subject with the subject guide to help them with at-home use and ask them to use the device between 7 to 8 hours per day. They will also ask them to open the Quell App once a day while the device is connected to cellular data or Wi-Fi to transfer the data to the Quell Health account. If the subject plans to use cellular data, the coordinator will setup the Quell App to allow the use of cellular data in the settings.

The coordinator will review the Edema Symptom Daily Diary, Edema Symptom Inventory Week Recall, and Edema Symptom Inventory-Week Recall 0-10 Scale forms and teach the subject how to complete them.

The coordinator will perform the ankle range of motion and lower limb sensation tests and measure the subject's lower limbs using the volumeter and tape measure.

The subject will complete the visit related patient-reported outcome measures (PROs) at the study visit if they were not completed previously using the REDCap link.

Weeks 1-3: (subject will do at home)

- Subject will use the Fitbit Device at all times.
- Subject will use the TENS device for 7 to 8 hours / day either day, night, or asleep.
- Subject will complete the Edema Symptom Daily Diary, Edema Symptom Inventory Week Recall, and Edema Symptom Inventory-Week Recall 0-10 Scale.

Phone Call 1: (Day 7, up to +2 days)

- AE assessment: The coordinator will ask the subject using an open-ended question whether any new symptoms have occurred since starting the study. If so, the coordinator will record the AE in the **AE form** in REDCap.
- Adherence discussion: The coordinator will discuss any adherence problems observed in the data from the Quell App.
- Reminder 3: remind the subject (and record in the **Telephone Contact Form**):
- To complete at-home (paper) PROs for Week 2 (Days 7-14).

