Page 15 of 26

Table 3: Edema schedule of data collection.

| FORMS | Screening | Prebaseline period | Treatment period | Treatment period Endpoint |
|---|-----------|-----------------------|------------------|---------------------------------|
| Subject Forms (REDCap or paper) | | | | |
| On Study | | X | | |
| Edema Symptom Daily Diary | | | X | X |
| Edema Symptom Daily Diary-Pre-baseline ¹ | | X | | |
| Impression of Change in Edema Symptoms | | | | X |
| Expectation Questionnaire ³ | | | X | |
| CIVIQ 20 ³ | | | X | X |
| LYMQOL ³ | | | X | X |
| PROMIS Fatigue ³ | | | X | X |
| Edema Interference Questionnaire ³ | | | X | X |
| General Impression of Edema ³ | | | | X |
| General Impression of Activity ³ | | | | X |
| Edema Symptom Inventory-Week Recall | | X | X | X |
| Edema Symptom Inventory-Week Recall 0-10 Scale | | X | X | X |
| Treatment period Endpoint-Qualitative Feedback | | | | X |
| Coordinator Forms (REDCap or paper) | | | | |
| Eligibility checklist (Medical record, Clinicianreported, and Patient-reported items) ¹ | X | | | |

Page 16 of 26 Version Date: 12/8/2020

| Consent form | X | | |
|--------------------------------------|---|---|---|
| Clinical Record Information | X | | |
| TENS Device Settings | | X | |
| Coordinator Lower Limb Swelling | X | X | X |
| Volumeter Measurements | | X | X |
| Lower Limb Sensation Threshold | | X | X |
| Ankle Range of Motion | | X | X |
| COVID pre-screen form | X | X | X |
| Telephone Contact | X | X | X |
| Adverse Event (AE) form ² | | | X |

¹ Forms are completed during the weeks 1, 2, and 3 and being returned by mail to the research team.

General policies regarding contacting subjects: If subjects have chosen to be contacted by email but do not respond to email reminders, they will be called up to 2 times for that specific reminder. If a subject does not attend a phone Call or in-person visit, they will be called up to 3 times to try and reengage the subject in the study. If any phone calls are interrupted or stopped short for any reason, including technological difficulties, a subsequent phone call will be setup to complete the necessary research tasks. Rescheduling of visits can occur up to 1 week after the original visit was scheduled, which will be scheduled within the time-frame indicated in the protocol section for each visit.

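### Does the plan need a separate analysis rule for Impression of Change in Edema Symptoms, which has no Baseline value?

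*Combined protocol and SAP*

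**What the plan says.** Section 16 (Aim 2, item 1) states that the two primary preliminary efficacy outcomes will be "assessed using Wilcoxon sign-ranked test comparing the outcomes from Baseline and Treatment Endpoint". Item 2 extends this to the secondary tier in one sentence: "Similar analyses to those in the primary preliminary efficacy aim will be used for the secondary efficacy outcomes".

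Section 4, under "Potential Efficacy (secondary) Objective" assessments and the patient-reported measures that follow, lists three secondary outcomes: tape measurements, the Impression of Change in Edema Symptoms form, and the LYMQOL.

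The Impression of Change form is described as "asking subjects to report whether they have experienced changes in the symptoms". It is scored "1 = very much improved, 7 = very much worse", and the fourth of its seven anchors means no change. Table 3 in section 8 shows it as "Impression of Change in Edema Symptoms | | | | X", where the single mark falls in the Treatment period Endpoint column.

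**The concern.** Read literally, the secondary rule cannot be applied to this form. A Baseline-to-Endpoint comparison needs two values per subject, and the schedule supplies one. The plan does not give the value to test against, does not say that the test becomes a one-sample test, and does not say what happens to answers of no change.

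If those choices were open, they would be made in a single-arm study whose team reviews accumulating data (section 15, Data Monitoring), so the analysis could be picked with responses in view. On a seven-point item where many subjects may report no change, the p-value could depend on the choice. The reading of one of three secondary outcomes, and one of two secondary patient-reported outcomes, would be at stake.

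**Working it through.** The plan gives no figure to reproduce on this point. The sample size of 52 is justified by feasibility, with no power, effect size or alpha stated.

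**Step 1. Which secondary outcomes have a pair?**
- Tape: measured at Visit 2, where the coordinator measures the "lower limbs using the volumeter and tape measure", and again at Visit 3. A pair exists.
- LYMQOL: marked in Table 3 under both Treatment period and Endpoint. At Visit 2, "The subject will complete the visit related patient-reported outcome measures (PROs) at the study visit" unless already done online. A pair exists.
- Impression of Change: Endpoint only. No pair exists, and a rating of change since treatment began would mean nothing before treatment.

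The literal mismatch is therefore confirmed for one outcome of three.

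**Step 2. What does a similar analysis mean for a change rating?** For paired data the signed-rank test uses d = Endpoint − Baseline and asks whether d is centred on 0. This form records the change directly, with no change coded 4, so d = score − 4. Pairing every score with a constant 4 and running the paired test gives the same p-value as the one-sample test against 4.

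Other references fail at once. Take assumed answers balanced around no change (counts 1, 4, 9, 24, 9, 4, 1 for scores 1 to 7; n = 52). A reference of 4 gives p = 1.0. A reference of 0 (off the scale) or 1 (very much improved) gives p of about 2 to 3 × 10⁻¹⁰, a rejection when there is no effect. The reference is not a live choice.

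**Step 3. How much does the treatment of 4s matter?** Two assumed sets of counts, n = 52, two-sided, normal approximation without continuity correction. W is the rank sum of those who worsened, and z = (W − mean)/SD.

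*Scenario A: 4, 8, 8, 16, 14, 2, 0 (20 improve, 16 unchanged, 16 worsen).*
- 4s dropped: 36 remain, with mid-ranks 11.5, 27.5 and 34.5 for distances 1, 2 and 3. W = 14 × 11.5 + 2 × 27.5 = 216; mean = 36 × 37/4 = 333; SD = 61.71; z = −117/61.71 = −1.896; p = 0.058.
- Pratt (4s ranked, then left out of the sums): each mid-rank rises by 16. W = 14 × 27.5 + 2 × 43.5 = 472; mean = 621; SD = 106.96; z = −1.393; p = 0.164.

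*Scenario B: 2, 6, 14, 22, 5, 2, 1 (22 improve, 22 unchanged, 8 worsen).*
- 4s dropped: 30 remain, with mid-ranks 10, 23.5 and 29. W = 5 × 10 + 2 × 23.5 + 1 × 29 = 126; mean = 30 × 31/4 = 232.5; SD = 47.01; z = −2.265; p = 0.023.
- Pratt: each mid-rank rises by 22. W = 5 × 32 + 2 × 45.5 + 1 × 51 = 302; mean = 562.5; SD = 104.67; z = −2.489; p = 0.013.

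An exact sign test, which the plan does not name, gives 0.62 in A (20 v 16) and 0.016 in B (22 v 8).

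In A every result lies above 0.05, and in B every result lies below it. A is also an unfavourable case for agreement: 12 improvers score 1 or 2, while 14 of the 16 who worsen score 5, so the weight given to distance matters unusually much.

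**The case for a change.** The strongest case for a change is that settling the reference at 4 does not settle everything. Two competent analysts could still report 0.058 and 0.164 from the same data, and 0.62 if one of them used a sign test. Section 16 also limits its template elsewhere: the exploratory tier applies it to continuous outcomes only and gives the monofilament outcome its own test. The secondary rule has no such limit. With no blinding, no multiplicity adjustment and results meant to inform a decision on a randomised trial, fixing the choice in advance would cost very little.

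Some of this stands. The reference is unstated, and p-values within the signed-rank family can differ. The rest is weaker.
- The 0.62 comes from a test that discards the ranks, which is hard to call similar to the named one.
- Treatment of zero differences is not particular to this form. The plan gives no such rule for any signed-rank test, including the primary daily diary on its 1 to 5 scale. Dropping zeros is the standard form of the test.
- A fuller rule could do harm. Testing each item separately would add an unknown number of unadjusted tests, because the documents do not give the number of items. Mandating that no-change answers be dropped would remove 16 or 22 of the 52 subjects in the scenarios above, with no stated reason to prefer that to Pratt.

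**Conclusion.** The observation is accurate, but it is missing detail rather than an error. The plan calls for similar, not identical, analyses and names the test. The scale supplies the only sensible null value. An analyst following section 16 would run a one-sample signed-rank test against 4 and would not reach a wrong result by doing so.

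The effect is confined to one of three secondary outcomes in a single-arm study that section 16 itself calls exploratory. No decision threshold depends on this form. The p-value range within the named test is 0.058 to 0.164 in one assumed scenario and 0.013 to 0.023 in the other, with no change of conclusion at 0.05 in either. Those ranges rest on invented response counts and would differ with others, so a borderline data set could fall on both sides of 0.05. In an exploratory analysis without an alpha, that would not alter what the study can claim. No change to the plan follows.

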4. STUDY DESIGN

Experimental design

This study is single center, subject will receive a wireless TENS device. The treatment period will be 3 weeks in duration. All subjects will be allowed to keep the commercially-available device for use after the study. All subjects will be called (via phone) one month after completion of the Endpoint visit and asked if they are still using their commercial device.

The study will have a single arm. The coordinator will introduce the study device, be available to answer questions about the device, and assess adverse events. Subjects will be told that we are testing whether TENS, which has shown promise in some patients but needs to be tested formally, has an effect on lower limb swelling.

Page 3 of 26

Study measures

Demographic data will be collected from the medical record including age, sex, BMI, medications they are taking that could affect lower limb edema, history of diabetes, cancer, deep vein thrombosis, post thrombotic syndrome, peripheral neuropathy, and hypertension.

Feasibility (primary)

- (1) Screen failure and patient refusal rates will be assessed using study records.
- (2) Outcome measure completion rates will be assessed using study records.

Feasibility (secondary)

(1) Treatment adherence will be evaluated using data from the TENS device's Quell App (i.e., the number of treatment sessions/day and the time that the device was in contact with the skin). The Quell Health account within the Quell App for each subject will be setup at the Baseline visit using a de-identified, unique dummy email address created for the study to protect subjects' privacy.

Feasibility (exploratory)

(1) Potential reasons for low treatment adherence will be captured using structured qualitative interviews and used to assess potential reasons for low adherence and ways to improve a future study.

Potential Efficacy (primary) Objective

assessments:

(1) Swelling The volume of water displaced by the combination of the foot and ankle, and the entire lower limb below the knee of the most affected limb at baseline will be measured using a Volumeter, which is a water displacement measurement device. The volumes will be recorded in **Volumeter Measurements** form.

Volume measurements have been used in a successful trial of compression stockings for flightinduced peripheral edema. 12

Patient reported outcome measure (PRO):

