- (1) Lower limb sensation will be measured using a monofilament threshold test (i.e., lower limb sensation test)¹⁴ on the most affected limb at baseline. The scores will be recorded in the **Lower Limb Sensation Test Scoring Sheet**.
- (2) Activity will be measured using the number of steps taken and period of time the subject is sedentary with a Fitbit activity tracker and the TENS device's Quell App.
- (3) Ankle range of motion will be measured using a tape measure while the subject performs the weight-bearing lunge. The resulting measurements will be recorded in the **Ankle Range of Motion** form. This method has been shown to have good reliability when administered by a novice rater.¹⁵

Patient reported outcome measure (PRO):

(1) Fatigue will be assessed using the **PROMIS Fatigue** – Short Form. The PROMIS Fatigue – Short Form was created using a multisite project developed by a clinically relevant and psychometrically quality of life assessment tool for adults and children with neurologic disorders. The measure uses a verbal rating scale (VRS) with anchors "never", "rarely", "sometimes" "often ", or "almost always" [1 = never, 5 = almost always].

Page 5 of 26

Mood, Stigma, and Sleep will be assessed using modified version of Chronic Venous Disease Quality-of-Life Questionnaire (CIVIQ 20), which was developed based on a clinically relevant and psychometrically quality of life assessment tool for adults. The validity was assessed using Cronbach's alpha coefficients and multi-trait/multi-item matrix analyses. The CIVIQ 20 consists of a VRS asking subjects to report whether they have experienced any of specific emotions over the past three weeks using a 1 – 5 Likerttype scale, with anchors "not at all", "a little", "moderately", "a lot", or "completely" [1 = not at all, 5 = completely].

Single-Item Questions:

- (1) **Expectation Questionnaire**. The subject's expectation of device efficacy will be assessed by asking the subjects: "How much do you expect the TENS device will improve your edema symptoms?" using a 1-5 Likert-type scale, with anchors "not at all", "a little bit", "quite a bit", "very much", or "completely" [1 = not at all, 5 = completely].

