4.1. SUBJECT POPULATION

Fifty-two subjects will be enrolled in the study. We anticipate that 150 potential subjects will be approached in order to reach this goal (i.e., 1 in 3 potential subjects will be eligible and choose to enroll). If subjects drop out after enrollment, they will not be replaced.

Vulnerable populations, including children, pregnant women, those who are unable to perform consent, and prisoners will not be eligible for this study.

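### Exploratory item 2 cuts the paired monofilament threshold score to improved or not and names Fisher's exact test, which has no second group in a single-arm study

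*Combined protocol and SAP*

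**What the plan says.** **Design.** Section 4 states "The study will have a single arm".

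**Measurement.** In Section 4, under the exploratory objective assessments, lower limb sensation "will be measured using a monofilament threshold test (i.e., lower limb sensation test") on the limb most affected at baseline, and "The scores will be recorded in the" scoring sheet. Section 8 schedules the test at Visit 2 ("The coordinator will perform the ankle range of motion and lower limb sensation tests") and again among the physical assessments at Visit 3. The schedule of data collection (Table 3) lists the form accordingly. Each completer therefore supplies a pair of ordered scores on one limb.

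**Analysis.** Section 16 treats exploratory outcomes in two ways:

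- Item 1: "Similar analyses to those in the primary preliminary efficacy aim will be used to assess changes between Baseline and Treatment Period Endpoint", restricted to the continuous exploratory outcomes. The primary method it refers to is the Wilcoxon signed-rank test, which the plan also applies to the Edema Symptom Daily Diary, a rating from 1 to 5.
- Item 2: "The percentage of subjects whose monofilament threshold improves between Baseline and" an endpoint labelled Double-blind, compared by Fisher's exact test. No second group or reference percentage is named.

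**Size.** "Fifty-two subjects will be enrolled in the study" (Section 4.1), and dropouts are not replaced. Section 16 justifies this number by feasibility. It gives no alpha, power, effect size or SD for the monofilament outcome.

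**The concern.** Item 2 has two linked faults.

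1. **The test cannot be run as written.** Fisher's exact test compares proportions between groups, and this study has one group. The reference to a double-blind endpoint matches nothing else in the design.
2. **The summary throws information away.** A one-step and a larger improvement count the same, and a subject who does not change counts the same as one who gets worse. Correcting only the test would leave this second fault in place.

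Section 1 (Aim 2) sets out to estimate the potential effect of TENS on sensation, among other outcomes. A percentage improved does not say how far thresholds moved, and without the percentage worsened it does not show the balance of change either. The documents give no responder definition or other reason for the cut. An ordinal scale is no reason within this plan, because the ordinal diary is analysed by signed ranks.

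**Working it through.** **Step 1: Fisher's test with one group.** The only available table has one row, (x improved, n − x not improved). Its margins equal its cells, so only one table is possible and p = 1 whatever x is. The plan gives no power figure to reproduce, and none can be computed for the named test.

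**Step 2: what the percentage hides.** Take 52 pairs with 20 improved, so the reported figure is 20/52 = 38%. If the other 32 are unchanged, a two-sided exact sign test on 20 against 0 gives p = 2 × 0.5^20 ≈ 0.000002. If the other 32 worsened, z = (32 − 20)/√52 = 1.66 in the direction of harm, p ≈ 0.10. The percentage is the same and the conclusions are opposite.

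Testing the percentage against 50% is no repair. With no effect and a share t unchanged, the expected percentage improved is (1 − t)/2: 37% at t = 0.26, 31% at t = 0.38, 16% at t = 0.68. In simulated null trials with 52 pairs, a test against 50% rejected in 42%, 78% and 100% respectively.

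**Step 3: cost of the cut, under assumptions.** The document supplies only n = 52 with no replacement. The following are assumed:

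- changes are normal, rounded to whole threshold steps, with SD 0.5 to 3 steps;
- the standardised mean change d is 0.3, 0.4 or 0.5;
- alpha is 0.05 two-sided;
- 44 to 52 pairs are evaluable (44/52 = 85%).

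The signed-rank test (zeros dropped, tie-corrected normal approximation) is set against a sign test on improved versus worsened. The sign test stands in as a valid paired binary analysis. It is run in exact form and in asymptotic (McNemar-type) form.

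Power in % at n = 52, for d = 0.3 / 0.4 / 0.5 (4,000 trials per setting):

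| SD (steps) | unchanged | signed-rank | exact sign | asymptotic sign |
|---|---|---|---|---|
| 0.5 | 62–66% | 44.9 / 69.1 / 87.6 | 36.1 / 59.5 / 81.4 | 44.4 / 68.6 / 87.2 |
| 0.7 | 47–51% | 48.9 / 74.3 / 90.4 | 38.4 / 63.9 / 84.1 | 47.7 / 73.3 / 89.3 |
| 1.0 | 34–37% | 53.3 / 76.3 / 91.3 | 41.6 / 64.1 / 83.7 | 49.3 / 71.4 / 88.4 |
| 1.5 | 23–25% | 54.5 / 79.3 / 93.4 | 39.7 / 65.2 / 84.4 | 45.4 / 70.8 / 87.7 |

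Gain of signed-rank, in points (differences taken before rounding):

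| SD (steps) | over exact sign | over asymptotic sign |
|---|---|---|
| 0.5 | 8.8 / 9.6 / 6.1 | 0.5 / 0.5 / 0.4 |
| 0.7 | 10.5 / 10.4 / 6.3 | 1.2 / 1.0 / 1.0 |
| 1.0 | 11.7 / 12.2 / 7.6 | 4.0 / 4.8 / 2.9 |
| 1.5 | 14.8 / 14.0 / 9.0 | 9.1 / 8.5 / 5.6 |
| 3.0 (1,500 trials) | 18 / 19 / 12 | 12 / 14 / 8 |

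**Step 4: which comparison is fair.** For SD 0.5 to 1.5, null rejection at n = 52 was 0.046–0.054 for signed-rank, 0.045–0.057 for the asymptotic sign test and 0.026–0.035 for the exact sign test. The last column therefore isolates the loss of scale. The column beside it also contains the conservatism of the exact test. Size-matched, the range is about 0 to 14 points; against the exact test it is about 6 to 19. The same ranges hold, within simulation error, at 44 pairs. That error for a power near 50% is √(0.25/4,000) = 0.8 points with 4,000 trials and √(0.25/1,500) = 1.3 points with 1,500.

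**Step 5: sensitivity to shape.** With continuous normal changes and no ties, the gain at n = 52 is 18, 23 and 16 points for d = 0.3, 0.4 and 0.5. With heavy-tailed (t, 3 df) changes it is 9, 5 and 1. At d = 0.8 it is at most 1 point in every setting at n = 52.

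**The case against.** The strongest reply is that this is one exploratory outcome in a feasibility study. No power is planned, multiplicity is not adjusted, and nothing in the documents makes progression depend on it. A responder percentage is easy to read. Item 1 is reserved for continuous outcomes, and a monofilament threshold is arguably ordinal. The scores are recorded, so a median change could still be reported. If the kit has few grades and most subjects do not move, the signed-rank test gains almost nothing.

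Much of this stands. The consequence is modest, and the gain can be close to zero. The scale argument is weak, because the same plan uses signed ranks for a five-point rating. Being able to report a median later is not the same as planning it.

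A reader might infer that the cut costs this trial a definite amount of power, say 7 to 19 points. The documents do not support that. They give no SD, effect, alpha or tie rate, and the scoring sheet is not reproduced, so the number of grades is unknown. Figures of that order also rely on the exact sign test, whose true size here is about 3%. Finally, the loss is measured against a sign test that stands in for the plan's own test, which has no computable power.

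**Conclusion.** The point holds as a minor analysis defect. From the documents alone, item 2 names a two-group test in a one-group study, refers to an endpoint that does not exist here, discards the size of each change, and pools unchanged with worsened subjects. No reason is given, and a suitable paired method is already in the plan.

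The cost in power is a conditional range and not a property of the plan: about 0 to 14 points against a size-matched sign test, or about 6 to 19 against the exact sign test. It rests on whole-step changes with SD 0.5 to 3, shifts of 0.3 to 0.5, two-sided 0.05 and 44 to 52 pairs. When about half or more of the subjects are unchanged, the size-matched gain is about 1 point or less. A reader should not conclude that Aim 2 fails or that a real effect on sensation would probably be missed. The firmer argument is about estimation: a percentage improved cannot say how far, or on balance in which direction, thresholds moved.

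**What to change.** In Section 16:

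- Move the monofilament score into Exploratory Analysis 1, and extend that item's wording beyond continuous outcomes so that it covers this score.
- Compare Baseline and Treatment Endpoint scores within subject with the Wilcoxon signed-rank test. State how zero changes are handled and which direction of change is an improvement.
- Report the median change in threshold steps with a 95% confidence interval.
- Show the percentages improved, unchanged and worsened as description only. They are needed beside the median, which is zero by construction when more than half of the subjects are unchanged.
- Delete Fisher's exact test, and replace Double-blind Endpoint with Treatment Period Endpoint.

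The cost is a sentence or two of text. No new data, visits or subjects are required. The one downside is that a median step change is slightly less intuitive than a percentage, and the percentages remain on display.
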